### 3.2.1 Sample Size

Sufficient individuals will be screened to enrol approximately 195 subjects assuming an estimated 25% drop out rate. It is believed that for this study 147 completed subjects are deemed sufficient to observe an improvement in QoL.

There were no previous similar studies measuring MVPA coupled with daily use of a diclofenac gel. Thus, the effect size was chosen based on literature review to detect even mild improvement in QoL factors: “An effect magnitude between 0.2 and 0.5 indicates mild improvement, between 0.5 and 0.8 indicates moderate improvement, and greater than 0.8 indicates considerable improvement in symptoms and QoL.” The sample size was based on a significance level ( $\alpha$ ) = 0.05, Power ( $1-\beta$ ) = 80%, and a standardized effect size of 0.25

Literature review also indicated that QoL scores are not normally distributed. Subjects with worse baseline symptoms showed larger improvement in QoL scores. Therefore, a two-sided non-parametric Wilcoxon Signed Rank test calculation was performed.

Using the above parameters, we obtain a sample size  $N = 195$  to retain the required 147 completed subjects. Therefore, it has been determined that 195 eligible subjects will be recruited for the trial, with an anticipated 147 study subjects expected to successfully complete the study.

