## 7.4 Analysis Variables

### 7.4.1 Disposition

Subject disposition data are collected on the 'Study Termination' eCRF page. Subjects are recorded as "Completed", "Screening failure", or "Early withdrawal". The date of the disposition event, date of last application of study drug and, if applicable, the date of death is recorded.

If applicable, the primary reason for discontinuation may include any of the following:

- Adverse Event (with a drop down to specify the AE number);
- Death;
- Inclusion not met/ Exclusion criteria met;
- Lack of efficacy;
- Lost to follow-up;
- Non-compliance with study drug;
- Occurrence of pregnancy;
- Physician's decision;
- Protocol violation;
- Withdrawal of consent;
- Withdrawal due to no pain;
- Other (with a free text to specify).

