## 8. Analysis Methods

### 8.1 General Methods

Post-Text TLFs are provided in collated electronic PDF files.

For continuous variables, the mean, standard deviation, minimum, median and maximum are presented, together with the total number of observations and the number of missing and non-missing values. Unless otherwise specified, minimum and maximum values are reported to the same number of decimal places as the recorded measurements; mean and median are reported to one more decimal place and standard deviation one additional decimal place more than the mean.

For categorical variables, absolute and relative frequencies are reported. Relative frequencies are based on all observations and reported as percentages to one decimal place. Unless otherwise specified, percentages are based on the number of subjects with data and are not calculated for missing categories.

Adverse events are reported on a per-subject basis, i.e. if a subject reported several events coded to the same coding term the subject is counted only once at the respective level of display. The percentages are calculated using the number of subjects in the population Analysis Set as the denominator.

All hypotheses are tested at a 5% level of significance using a two-sided test unless otherwise specified.

P-values are rounded to three decimal places. If a p-value is less than 0.001 it is reported as "<0.001." If a p-value is greater than 0.999 it is reported as ">0.999.

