#### 8.2.2 Primary Analysis

The primary efficacy endpoint is the average MVPA at Days 7, 14 and 21 as detailed in section 7.4.7.1.

The primary analysis will follow a hierarchical approach as follows:

1. A Mixed Model with Repeated Measures (MMRM) is used to analyse the change from baseline in MVPA average minutes as the response variable with baseline as a fixed effect. Subjects will be included as a random effect, and timepoint will be treated as a

repeated measure within each subject (with compound symmetry structure between visits). If the parameter for the intercept is found to be statistically significant (p-value < 0.05), then the second model below will be used.

2. A Mixed Model with Repeated Measures (MMRM) is used to analyse the change from baseline in MVPA average minutes as the response variable with baseline and timepoint (with unstructured covariance structure between visits) as fixed effects. Adjusted means for each timepoint will be presented along with p-values and 95% confidence intervals (CIs) for the mean change from baseline in MVPA.

Other than the global test for an overall change from baseline (i.e., intercept), there will be no other adjustment for multiplicity. If data are found to be non-normal, the Friedman Test will be used. If the Friedman test is found to be significant then Wilcoxon Signed Rank Pairwise Tests are used for each week comparison.

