### 8.2.5 Statistical/Analytical Issues

#### 8.2.5.1 Handling of Dropouts or Missing Data

In the derivation of endpoints there is no replacement of missing data except for adverse event dates as detailed in section 7.2.2.

The primary and secondary analysis method employs mixed-model with repeated measures analysis techniques which use information from the observed data, likelihood-based estimation, subject-specific effects and the within-subject correlation structure to provide information about the unobserved data (although missing data are not explicitly imputed). This analysis uses the available data to provide information about the unobserved data and estimates the treatment effects assuming the withdrawn subjects has the same statistical behaviour as those who continue. Data is not imputed for this type of analysis.

Missing data due to general dropout/withdrawals will be assessed on an ongoing basis during the study. Any further sensitivity analyses needed due to missing data will be reviewed at the time of data review.

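### For NRS and the WOMAC scores, the non-normality fallback replaces the MMRM with rank tests that discard partial data, so the plan's only missing-data rationale no longer applies

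*SAP*

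**What the plan says.** - **Fallback.** SAP 8.2.2 fits an MMRM to change from baseline with baseline as a covariate, then adds: "If data are found to be non-normal, the Friedman Test will be used". If Friedman is significant, signed-rank tests follow for each week. Nothing says the MMRM is kept. No normality test or threshold is given, and it is not stated whether the check is on the data or the residuals.
- **Scope.** SAP 8.2.3 analyses the listed secondary endpoints the same way. They include NRS, the three WOMAC subscales and the WOMAC Global Score at Days 7, 14 and 21.
- **Missing data.** SAP 8.2.5.1 states: "The primary and secondary analysis method employs mixed-model with repeated measures analysis techniques which use information from the observed data, likelihood-based estimation". It rules out replacing missing endpoint data and leaves sensitivity analyses to the data review. The WOMAC rule in SAP 7.4.7.2 covers missing items, not missing questionnaires.
- **Expected distribution.** SAP 3.2.1 says: "Literature review also indicated that QoL scores are not normally distributed".
- **Population.** SAP 6.1 admits a subject to the mITT set with one post-baseline WOMAC or EQ-5D-5L response and uses that set for all efficacy analyses.
- **Reasons for leaving.** SAP 7.4.1 lists lack of efficacy and "Withdrawal due to no pain".
- **Tracker endpoints.** SAP 8.2 admits only subjects with at least three valid days at baseline and at least three in each post-baseline week. NRS and WOMAC have no equivalent rule.

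**The concern.** SAP 8.2.5.1 has one defence against dropout: a likelihood model in which a subject's earlier values inform the later weeks. For the five questionnaire scores, that model is replaced if the data look non-normal, which the SAP itself suggests is likely for QoL scores. The replacement has no missing-data provision.

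The question answered then depends on a loosely defined normality check. The MMRM estimates the mean change in all subjects who contribute data, provided dropout depends only on observed values. The rank tests describe those still answering at that week. The listed reasons for leaving can be related to outcome in either direction, so later-week results could be too favourable or too unfavourable.

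**Working it through.** **1. The plan's own figures.** SAP 3.2.1 gives α = 0.05, power "80%, and a standardized effect size of 0.25", and states that "a two-sided non-parametric Wilcoxon Signed Rank test calculation was performed", "assuming an estimated 25% drop out rate". The one-sample normal formula gives ((1.960 + 0.842)/0.25)² ≈ 126. Noncentral t gives 128. Dividing by 0.864, the minimum asymptotic relative efficiency of the signed-rank test (my assumption about the method used), gives 146 to 149, which agrees with 147. For enrolment, 147/0.75 = 196 and 195 × 0.75 = 146.25, which agrees with 195 apart from rounding. The effect of 0.25 SD and dropout of 25% are used below.

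**2. What each method uses when a subject has Day 7 but not Days 14 and 21.**

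| Method | Day 7 value used? | Baseline covariate? |
|---|---|---|
| MMRM (SAP 8.2.2) | Yes, and it informs Days 14 and 21 | Yes |
| Standard Friedman | No, incomplete subject dropped | No |
| Signed-rank, Day 7 | Yes, for Day 7 only | No |
| Signed-rank, Days 14 and 21 | No | No |

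If all 25% leave after Week 1, Friedman and the Week 3 test rest on about 146 of 195 subjects, and about 49 Day 7 values inform neither.

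**3. How easily the fallback could be triggered.** Integer scores tend to fail a formal normality test. I rounded normal draws to whole numbers, n = 150, with assumed SD 2 (NRS-like) or 1.5 (stiffness-like). Shapiro-Wilk rejected at 5% in all 1,000 runs of each. The SAP does not name this test, so this shows only that the trigger is plausible.

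**4. Size, as an illustration.** Assumptions not in the documents: normal weekly changes with SD 1, between-week correlation ρ = 0.6, all dropout after Week 1, and log-odds of leaving linear in the Week 1 change with slope s per SD. Positive change means improvement.

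Let z be the standardised Week 1 change and p(z) = 1/(1 + exp(−(b + s·z))), with b set so that the mean of p is 0.25. The Week 1 shift among stayers is δ = E[z(1 − p)]/0.75. Because exit depends only on Week 1, the Week 3 mean among stayers is 0.25 + ρδ. Numerical integration gives |δ| = 0.120 for |s| = 0.5 and 0.213 for |s| = 1.

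| Who leaves | \|s\| | Week 3 mean, stayers | Using Week 1 data from all |
|---|---|---|---|
| Poor responders | 0.5 | 0.25 + 0.6 × 0.120 = 0.32 | 0.25 |
| Poor responders | 1 | 0.25 + 0.6 × 0.213 = 0.38 | 0.25 |
| Unrelated | 0 | 0.25 | 0.25 |
| Good responders | 0.5 | 0.25 − 0.6 × 0.120 = 0.18 | 0.25 |
| Good responders | 1 | 0.25 − 0.6 × 0.213 = 0.12 | 0.25 |

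The last column regresses Week 3 on Week 1 in stayers and averages the prediction over everyone, which is the MMRM principle without the baseline covariate. Simulation confirmed it.

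**5. Sensitivity.**
- *Correlation.* With ρ from 0.4 to 0.8, the stayers' mean runs from 0.25 + 0.4 × 0.120 = 0.30 to 0.25 + 0.8 × 0.213 = 0.42, or from 0.20 to 0.08 in the other direction.
- *Earlier dropout.* If half the dropout occurs before Day 7 and is unrelated to outcome, the later exit rate is 12.5/87.5 = 14.3%. Then |δ| = 0.127 at |s| = 1, and the mean is 0.25 ± 0.6 × 0.127 = 0.33 or 0.17.
- *Exit driven by the unobserved Week 3 value,* |s| = 1. Stayers' means are 0.25 ± 0.213 = 0.46 or 0.04. The estimate using Week 1 is 0.39 or 0.11, so only about a third of the bias is removed.

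**The case against.** The strongest objection concerns reach. The sentence sits in the primary analysis section, so a reader might infer that the primary MVPA result is exposed. The documents do not support that. On the plain reading of SAP 8.2, every subject in a tracker analysis has all three weekly values before either method runs. For MVPA, steps, sedentary ratio, gait and morning stiffness the fallback therefore costs no partial data. The MMRM there also describes only subjects who stayed and wore the device. Only if the wear rule were meant week by week would MVPA be affected.

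A reader might also infer a known, large bias that the MMRM would cure. That is not supported either. The documents give no correlation, dropout timing or link to outcome. Step 4 assumes normal data, although the fallback applies when data are not normal. With right-skewed changes at slope 1 and poor responders leaving, the observed-case mean was 0.31 rather than 0.38. The Week-1-based estimate was 0.26 to 0.28 with right skew and 0.22 to 0.24 with left skew. Leaving because of no pain may reflect the state at exit rather than the last recorded score, and the MMRM then helps only in part.

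Protocol 8.1 asks subjects who stop the gel to stay for remaining assessments, which would limit the loss. Protocol 9.2.3, however, ends the study the day after last treatment if that comes earlier than Day 21. The two need reconciling. Finally, a subject whose only questionnaire is from Day 1 enters the mITT set but contributes no Day 7, 14 or 21 value to either method.

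These points narrow the concern and make its size conditional. They do not answer the conflict between SAP 8.2.2 and 8.2.5.1 for NRS and WOMAC.

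**Conclusion.** The concern holds for five tested secondary endpoints: NRS and WOMAC Pain, Stiffness, Physical Function and Global. If the fallback is triggered, the SAP 8.2.5.1 rationale no longer describes the analysis, and partial data that the mITT definition admits are set aside.

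Under the step 4 assumptions, the Week 3 observed-case mean is off by 0.07 to 0.13 SD in either direction against an assumed effect of 0.25 (0.072/0.25 = 29% to 0.128/0.25 = 51%). This is an illustration, not a forecast. The bias is zero if dropout is unrelated to outcome and smaller if part of the dropout precedes Day 7. The MMRM removes only part of it if exit depends on unobserved later values.

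For primary MVPA and the other tracker endpoints, the fallback adds no dropout loss under the plain reading of SAP 8.2. This is a cheap improvement to the secondary analyses and does not challenge the primary result.

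**What to change.** In SAP 8.2.3, for NRS and the WOMAC scores, replace the inherited fallback with:

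> If residuals are clearly non-normal, the MMRM on untransformed change from baseline is retained as the main analysis with an empirical (sandwich) variance or subject-level bootstrap confidence intervals; signed-rank tests on observed changes are reported as supportive only.

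Two cautions:
- Do not use a log transformation of change scores, since changes can be zero or negative.
- Do not state in SAP 8.2.2 that subjects with incomplete timepoints contribute to the MVPA analysis while the SAP 8.2 wear rule stands. One added sentence should say whether that rule applies per subject or per week.

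The cost is SAP wording and a little extra programming on the existing model, with no new data. The downside is somewhat lower efficiency than rank tests under heavy tails; the supportive signed-rank results remain available for comparison.

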### 8.2.3 Secondary Analysis

The following secondary endpoints are analysed in the manner as described for the primary endpoint described in section 8.2.2:

- Change from baseline on Days 7, 14, and 21 in Daily Average number of steps taken.
- Change from baseline on Days 7, 14, and 21 in Ratio of sedentary/non-sedentary time.
- Change from baseline on Days 7, 14, and 21 in Gait, assessed through speed and step irregularity (measured via cadence and gait speed).
- Change from baseline on Days 7, 14, and 21 in Indices of morning stiffness (assessed through levels of mobility 30- and 60-mins post-wake).
- Change from baseline in self-reported pain intensity, assessed through Numeric Rating Scale (NRS) on Days 7, 14 and 21.
- Change from baseline in WOMAC Physical Function subscale on Days 7, 14, and 21.
- Change from baseline in the WOMAC subscales, Pain (composite) and Stiffness (composite) on Days 7, 14, and 21.
- Change from baseline in the WOMAC Global Score on Days 7, 14, and 21.

The secondary endpoint, study subjects' perceived ability to exercise more regularly, assessed using the WOMAC Physical Function subscale on Days 7, 14, and 21, will be analysed by exploring the correlation between WOMAC Physical Function subscale on Days 7, 14, and 21 and the average MVPA as detailed in section 7.4.7.1 (primary endpoint variable) graphically, by means of Spearman rank correlation.

The following secondary endpoints are analysed by descriptive statistics with no formal statistical hypothesis testing performed:

- MVPA on each day of the study (Baseline to final treatment day 21).
- Change from baseline in Karolinska Sleepiness Scale on Days 7, 14, and 21.
- Change from baseline in Health-related quality of life, EQ-5D-5L, on Days 7, 14, and 21.

### 8.2.4 Exploratory Analysis

#### Correlations between Voltaren usage, pain relief and mobility and quality of life indices throughout the trial.

Correlations between Voltaren usage, pain relief and mobility and quality of life indices will be explored graphically by means of a heatmap showing the extent of computed Spearman rank correlation coefficients among all QoL indices.

## Elapsed time from Voltaren Gel use to achieving time to meaningful pain relief to end of study

Time to meaningful pain relief is estimated using Kaplan-Meier method. This includes, patients with event, patients censored, time to meaningful pain relief (days), median with 95% confidence interval, Q1 and Q3. Time to event and censoring are derived as explained in section 7.4.7.3.

### 8.2.5 Statistical/Analytical Issues

#### 8.2.5.1 Handling of Dropouts or Missing Data

In the derivation of endpoints there is no replacement of missing data except for adverse event dates as detailed in section 7.2.2.

The primary and secondary analysis method employs mixed-model with repeated measures analysis techniques which use information from the observed data, likelihood-based estimation, subject-specific effects and the within-subject correlation structure to provide information about the unobserved data (although missing data are not explicitly imputed). This analysis uses the available data to provide information about the unobserved data and estimates the treatment effects assuming the withdrawn subjects has the same statistical behaviour as those who continue. Data is not imputed for this type of analysis.

Missing data due to general dropout/withdrawals will be assessed on an ongoing basis during the study. Any further sensitivity analyses needed due to missing data will be reviewed at the time of data review.

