### 9.2.3 End of Treatment Period/End Of Study

Subjects will have the option to discontinue treatment at their discretion. The reasons for discontinuing treatment will be captured whenever possible.

Subjects may choose to discontinue treatment if they feel that their symptoms do not warrant further use of the study product.

Subjects who wish to continue to use the study product will be prompted to discontinue treatment after the end of the study (28 days) and seek advice from their general practitioner for further assessment and treatment on their condition if needed.

Subjects will also be informed that the study will end on Day 21 (or the day after the last treatment, if earlier than 21 days), and will be asked to fill in an exit survey and perform final urine pregnancy test .

At the end of the study (Day 28), Actigraph device and the allocated product (used and unused) for this clinical study, should be returned to the Haleon Clinical Supplies Department or [CCI](#) using the return instructions provided.

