### **13.3.7 Handling of Dropouts and Missing Data**

Missing data due to general dropout/withdrawals will be assessed on an ongoing basis during the study. Any further sensitivity analyses needed due to missing data will be reviewed at the time of data review. Additional details will be provided in the data management plan and reporting and statistical analysis plan.

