## 1. Document History

Document Version	Date	Reason for changes
1.0	29OCT2024	Final version
2.0	05DEC2024	
Updates from the DRM:
 

• Section 7.1: Date of Last Study Treatment Administration updated include data collected in the End of Study Termination CRF

• Section 7.1: Study day definition updated to:

◦ Study Day = Date of assessment/event – Date of Baseline Visit.

• Section 7.1 Baseline derivation updated in line with new study day definition.

• Section 7.4.7 updated to exclude day 21 in the analysis due to Day 21 being a partial day.

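### The MVPA analysis is described as using all available data, but the SAP's wear rule makes it close to complete-case, and no sensitivity analysis tests its assumption about withdrawn subjects.

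*SAP*

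**What the plan says.** **Missing-data assumption.** SAP 8.2.5.1 describes a likelihood-based mixed model that imputes nothing, uses the available data and "estimates the treatment effects assuming the withdrawn subjects has the same statistical behaviour as those who continue".

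**Who is analysed.** The opening of SAP 8.2 restricts all tracker endpoints, including the primary one, to subjects who reach a wear threshold. This is three valid days at baseline and three in each post-baseline week, a valid day being one with at least 20 hours of wear.

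**Why subjects leave.** The reasons listed in SAP 7.4.1 include adverse event, "Lack of efficacy" and "Withdrawal due to no pain". SAP 3.2.1 sets enrolment at 195 to retain 147 completers, "assuming an estimated 25% drop out rate".

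**Sensitivity analyses.** Protocol 13.3.7 states: "Any further sensitivity analyses needed due to missing data will be reviewed at the time of data review". It then adds: "Additional details will be provided in the data management plan and reporting and statistical analysis plan". SAP 8.2.5.1 repeats the deferral. The SAP document history heads the version 2.0 changes "Updates from the DRM" and lists four: date of last treatment, study day, baseline derivation and Day 21. None concerns missing data.

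**Follow-up after stopping product.** Protocol 8.1 keeps a subject who is taken off product in the study for the remaining assessments. Protocol 9.2.3 says that "the study will end on Day 21 (or the day after the last treatment, if earlier than 21 days".

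**The concern.** The two SAP statements describe different analyses. A mixed model protects against dropout by using the early weeks of subjects who later leave. If everyone analysed must have all three weeks, no weeks are missing within the analysis set and that protection does nothing. The result is then a mean among those who stayed and wore the device.

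Even if early weeks are kept, the assumption needs withdrawal to depend only on data in the model. The model in SAP 8.2.2 contains MVPA, its baseline and timepoint. Withdrawal for lack of efficacy or for no pain is driven by pain, which the model does not contain. With a single arm, there is no comparison in which differential dropout could partly cancel.

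At stake is whether the reported mean change applies to the treated subjects as a whole. Nothing in the plan would show a reader how far the conclusion depends on this.

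**Working it through.** **1. What the wear rule does to an early leaver.** Take a subject with seven valid days in Week 1 who leaves on Day 9. Week 2 has at most two days, so the threshold fails. Under SAP 8.2 as worded the subject is out, including Week 1. Under SAP 8.2.5.1 the same Week 1 value should inform the model. Both cannot apply.

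**2. The plan's own figure.** Inputs from SAP 3.2.1: effect 0.25 SD, two-sided alpha 0.05, power 80%, signed-rank test, 25% dropout.
- Normal approximation, t-test: ((1.960 + 0.842)/0.25)² = 125.6.
- Dividing by a signed-rank efficiency of 0.864 (the minimum value, not stated in the documents): 125.6/0.864 = 145.4, so 146. The noncentral t version gives 148, and power 79.8% at 147.
- With the normal-data efficiency 3/π = 0.955, the noncentral t version gives 134.
- Dropout: 147/0.75 = 196, against the stated 195.

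The figures 147 and 195 therefore reproduce to within rounding, with 0.864 inferred.

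**3. Sensitivity of the mean to the dropouts.** Assumptions: 147 completers average 0.25 SD; 195 - 147 = 48 dropouts (24.6%) average m; SD is 1 in both groups; completers stand for the subjects analysed; the outcome is one mean change per subject.

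All-subject mean = (147 × 0.25 + 48 × m)/195. Two rough standard errors are used: 1/√147 = 0.0825, where imputed values add no information, and 1/√195 = 0.0716, where they count as observed.

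| Dropout mean m (SD) | All-subject mean (SD) | p, SE 1/√147 | p, SE 1/√195 |
|---|---|---|---|
| 0.25 | 0.250 | 0.002 | 0.0005 |
| 0.125 | 0.219 | 0.008 | 0.002 |
| 0 | 0.188 | 0.022 | 0.009 |
| -0.125 | 0.158 | 0.056 | 0.028 |
| -0.25 | 0.127 | 0.124 | 0.076 |

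**4. Tipping point.** Solve all-subject mean = 1.96 × SE.
- SE 1/√147: (0.1617 - 0.1885)/0.2462 = -0.11 SD, which is 0.36 SD below completers.
- SE 1/√195: (0.1404 - 0.1885)/0.2462 = -0.20 SD, which is 0.45 SD below completers.

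**5. False-positive rate of a completers-only test.** Suppose the true all-subject change is zero and completers exceed dropouts by 0.25 SD. Completers then average 0.2462 × 0.25 = 0.0615 SD, and 0.0615 × √147 = 0.75. A nominal 5% two-sided test rejects 11.6% of the time. The rate is 6.0% for a gap of 0.1 SD and 32% for 0.5 SD.

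**The case against.** **Outcome-related dropout need not break the model.** This is correct if leaving depends only on MVPA values in the model. The defence needs those values to be kept, which the wear rule prevents on its literal wording, and it does not cover withdrawal driven by pain.

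**The reasons pull both ways.** Subjects who leave without pain are probably responders; those who leave for lack of efficacy are not. The list also contains reasons unrelated to response, such as pregnancy, and the documents do not split the 25% by reason. This stands. A reader might infer that the estimate is one third too high (0.25/0.1875) or describes only responders and stayers. The documents do not support that; it needs every dropout to have zero change.

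**A loss of power.** A reader might also compute about 67% power by giving all 25% of dropouts zero change among 195 subjects. That rests on the extreme case and on the inferred 0.864. It becomes 72% with 0.955, 74% with 1.0, and about 81% on 0.864 if only half the dropouts have zero change. It is not the power of any analysis in the plan and should not be used.

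**The decision may lie elsewhere.** SAP 8.2.5.2 places data review decisions in an approved meeting report, which is not available here. Actual dropout is not given either; 25% is a planning figure. The point is therefore limited to the protocol and SAP.

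**No target was chosen.** Protocol section 4 marks estimands as not applicable, so centring imputations on baseline is one scenario and not the correct answer. This stands, and is why a tipping-point delta belongs beside it.

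**Conclusion.** The point holds as a gap in the plan and as a contradiction between SAP 8.2 and 8.2.5.1. On a literal reading the primary MVPA analysis is close to complete-case, and neither document names an analysis that tests what this assumes about subjects who leave. The direction of bias cannot be determined.

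At planning figures the conclusion is fairly resilient. Zero change in all dropouts lowers the mean by a quarter, from 0.25 to 0.19 SD, and significance survives. It is lost only if dropouts worsen to about -0.11 to -0.20 SD. These values assume SD 1 in both groups, 48 dropouts, an observed effect of exactly 0.25 SD and one mean change per subject. A smaller observed effect would leave less room. This is a cheap improvement and not a reason to distrust the primary model as such.

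**What to change.** 1. **Reconcile SAP 8.2 with 8.2.5.1.** Apply the three-valid-day rule week by week, so that subjects with a valid baseline and any valid post-baseline week contribute, at least in a sensitivity analysis. Without this, imputation has little to act on.
2. **Specify one sensitivity analysis in SAP 8.2.5.1**, before database lock or otherwise labelled post hoc. Use multiple imputation of weekly MVPA in all mITT subjects with a valid baseline. Centre weeks missing after withdrawal for lack of efficacy, adverse event, non-compliance or loss to follow-up on the subject's own baseline, and impute the rest as in the main model. Add a tipping-point delta and report the value at which the conclusion changes.
3. **Reconcile Protocol 8.1 with 9.2.3** on whether assessments continue after product is stopped, since this determines how much data is missing.

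The cost is SAP wording, a little programming and a possibly less favourable supporting result. The primary model does not change.
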